3.1.1 Minimum 3-Week and Up to 9-Week Screening Period

After signing an institutional review board (IRB)-approved informed consent document, screening will be performed within a minimum of 21 (3 weeks) days and up to 63 days (9 weeks) prior to Baseline (Visit 2). A review of screened patients to ensure safety and to confirm eligibility will be performed by an Enrollment Authorization Committee (EAC) prior to randomization (see [Section 4.1](#) and [Section 6.10](#)).

For patients requiring an amantadine washout period, two screening visits will be required during the screening period: Visit 1 and Visit 1.1. Visit 1, the first screening visit, will be performed up to 9 weeks/63 days prior to Baseline (Visit 2) and Visit 1.1 will be performed no later than on 3 weeks/ Day -21 days prior to Baseline (Visit 2) as defined in [Table 4](#).

For patients not requiring a washout period for any prohibited medication (see [Section 5.10.1](#)), only one screening visit will be required during the screening period: Visit 1. As much as possible, this visit should be performed 3 weeks/ 21 days prior to Baseline (Visit 2) as defined in [Table 4](#).

During the screening period (either during Visit 1 or Visit 1.1 depending on the need for amantadine washout), potential patients and any involved caregivers or study partners will be trained by a rater, a qualified study staff member to recognize the different motor states (“ON without dyskinesia,” “ON with no troublesome dyskinesia,” “ON with troublesome dyskinesia,” and “OFF”), and to complete a corresponding “ON/OFF” home diary.

After training, the study rater and the patient will complete an “ON/OFF” diary at half-hour intervals over a 4-hour period to ensure concordance of >75% between the evaluations (e.g., “ON, OFF and dyskinesia”) of the rater and the patient. During this concordance testing, patients must experience each of the motor states and at least one time period rated as “ON with dyskinesia”. After assurance of >75% concordance, the patients will complete the “ON/OFF home diary” at home during three consecutive 24-hour periods (72 hours total). The patients will send the completed diaries to the site (e.g., via fax, email) up to 1 week before

end of the screening period because these diaries will serve as the baseline motor home diary and for eligibility to participate in the study. Training may be repeated during the screening period to ensure concordance with the rater.

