4.1.1 Inclusion Criteria

Patients may be included in the study only if they meet all of the following criteria:

1. Male or female patients between 30 and 85 years of age, inclusive
2. Signed an IRB-approved ICF
3. Diagnosis of PD consistent with the UK Parkinson's Disease Society (UKPDS) Brain Bank Clinical Diagnostic Criteria
4. Hoehn and Yahr Stage 4 or less in the "ON" state such that the patient can complete the study assessments
5. Documentation of LID by the investigator
6. A score of 3 on 2 elements of the Unified Dyskinesia Rating Scale (UDysRS) part 4 – Disability Scale
7. Using the three consecutive 24-hour "ON/OFF" home diaries completed prior to Baseline (Visit 2), at least two half-hour time periods one between 8:00 AM and 5:00 PM of each 24-hour period are indicated as "ON with dyskinesia"
8. Patient and/or study partner must demonstrate during the screening period an ability to keep accurate home diary entries of PD symptoms ("ON, OFF, and dyskinesia") with >75% concordance with the study rater. During the 4-hour concordance testing, patient must experience all motor states: "ON", "OFF" and at least one period of "ON with dyskinesia"
9. Patients who are stable on a total daily dose of ≤ 200 mg amantadine must be off this treatment at least 4 weeks prior to the assessment of UDysRS part 4, the concordance testing and the completion of the three consecutive 24-hour "ON/OFF" home diaries which are performed during screening
10. All anti-PD treatments are stable for at least 28 days prior to Baseline (Visit 2), including a levodopa preparation administered no less than three times daily, with the same dosing regimen during the 12-week maintenance study treatment period

11. If taking allowed antidepressant or antipsychotic medication, must be on a stable dose for at least 28 days prior to Baseline (Visit 2) and must be kept constant during the study
12. Any other routine and allowed prescription/nonprescription medications and/or nutritional supplements taken regularly must be at stable dosages for at least 28 days prior to Baseline (Visit 2) and remain during study participation
13. Willing and able to comply with study requirements
14. Approval for entry into the study by an independent EAC (see [Section 6.10](#))

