5.10.1 Prohibited Medications and Substitution Alternatives

The medications in the excluded medications column of [Table 3](#) are not allowed within 6 weeks before Baseline (Visit 2) or during the study. By-class substitution alternatives (if available) are also provided in [Table 3](#).

Enrolled patients must be provided with all contact information in order to allow any prescriber to discuss medication changes with the clinical investigator team/medical monitor before making therapeutic decisions and prescribing new medications during the study.

Table 3 Prohibited Medications and Substitution Alternatives

Medication Class	Excluded medications	Substitution Alternatives
Anti PD/ PD-LID	apomorphine, mucuna pruriens , topiramate, amantadine, levodopa injection/infusion	Not applicable

Medication Class	Excluded medications	Substitution Alternatives
Antipsychotics	ziprasidone, clozapine, haloperidol, mesoridazine, thioridazine, pimozide, zuclopentixol, chlorpromazine, paliperidone, iloperidone, fluphenazine, prochlorperazine, trifluoperazine/trifluoperazine, flupentixol, benperidol, amisulpride, and sulpiride	aripiprazole, risperidone, olanzapine, quetiapine, thiothixene, acetophenazine, trifluoperazine, loxapine, tiapride, chlorprothixene, bromperidol
Antidepressants	Any tricyclic/tetracyclic antidepressant (e.g., amitriptyline, nortriptyline, imipramine, desipramine, doxepin, clomipramine, protriptyline, and amoxapine), Escitalopram, citalopram, trazodone >100 mg/day All triple reuptake inhibitors lithium (mood stabilizer)	SSRI/SNRIs: venlafaxine, paroxetine, duloxetine, sertraline, omipramol (opipramol), moclobemide, tranylcypromine, buspirone, reboxetine, dibenzepin, fluvoxamine Bupropion: special caution re: seizure risk, maximum 3 × 150 mg/day
Antiarrhythmics	disopyramide, procainamide, quinidine, flecainide, propafenone, amiodarone, dofetilide, ibutilide, sotalol	mexiletine, tocainide
Dopamine antagonists	All dopamine antagonists are prohibited (e.g., Reglan [metoclopramide])	Not applicable
Other ^a	astemizole, terfenadine, azithromycin, erythromycin, moxifloxacin, pentamidine, sparfloxacin, clarithromycin, chloroquine, halofantrine, bepridil, cisapride, domperidone, droperidol, levomethadyl, codeine, sevoflurane, tamoxifen, anagrelide, budipine, cotrimoxazole, fluconazole, levofloxacin, lidoflazine, loratadine, ondansetron, probucol, sertindole, terodililine, vandetanib	Clinician's choice and decision on a specific base-basis.

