Abbreviations: PD, Parkinson's disease; PD-LID, levodopa-induced dyskinesia in patients with Parkinson's disease; SNRI, serotonin-norepinephrine reuptake inhibitor; SSRI, selective serotonin reuptake inhibitor;

^a Due to either QT prolongation effects or metabolism by CYP2D6 into active metabolites

** Fluoxetine is allowed as it carries a conditional risk only for patients with congenital Long QT, hypokalemia or metabolic inhibitors.

Other:

- Use of all oral cannabinoids (including all preparations containing any cannabinoids, including cannabidiol, as well as prescribed oral medical marijuana and oral cannabidiol) with only an exception for topical formulations of cannabidiol, are prohibited within 28 days prior to Baseline (Visit 2) and during the study
- Amantadine is not allowed within 4 weeks prior to the UDyRS Part 4 assessment for eligibility, concordance testing, and completion of the 3 consecutive 24 hour "ON/OFF" home diaries during the screening period
- Apomorphine is not allowed within 28 days prior to screening and during the study

6 Study Assessments and Procedures

Before performing any study procedures, all potential patients will sign an IRB-approved- ICF. Patients will have the opportunity to have any questions answered before signing the ICF. The investigator must address all questions raised by the patient. The investigator or designee will also sign the ICF.

On-site (in-clinic) visits should be scheduled around the second (PM) study treatment daily dose within the time window of 11:00 AM through 5:00 PM and at consistent time points. Attempts will be made to schedule all study visits for an individual patient at approximately the same time of the day. The same in-clinic procedural timing will be kept for each of the in-clinic- visits for each patient. The in--clinic procedural flow for Baseline (Visit 2) is presented in [Appendix 13.1](#). The in-clinic procedural flow for Visits 3 to 7 is presented [Appendix 13.2](#). The second (PM) study treatment daily dose (at clinic) should be taken 6-10 hours after the first (AM) study treatment daily dose, which is taken at home, and not later than 5:00 PM.

A detailed schedule of study procedures/assessments is provided in [Table 4](#).

Table 4 Schedule of Assessments

Study Period ^a	Screening		Treatment Period							Down-titration	Safety Follow-Up
			Up-titration		Maintenance						
Study Week			Week 1 ^b	Week 5	Week 7	Week 10	Week 13	Week 16/ET ^c	Week 17 ^d	Week 18	

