- j. Patients' existing anti-PD medication regimens, including, but not limited to, levodopa oral preparations, must be maintained at a stable dose for at least 28 days prior to Baseline (Visit 2) and for the entire duration of the treatment duration period. During the 4-week titration period, for patients who suffer from symptoms indicating worsening of PD, the levodopa regimen may be adjusted until the regimen is optimal according to the Investigator's judgement. This optimal regimen must be obtained within the 4-week titration period and cannot be lower than the levodopa regimen at the time of screening. Allowed antidepressant or antipsychotic medication and any other routine allowed prescription/nonprescription medications and/or nutritional supplements taken regularly, must also maintained at stable dose for at least 28 days prior to Baseline (Visit 2) for the entire duration of the maintenance treatment duration period.
- k. Training of patients and study partners on recognition of motor state and "ON/OFF" home diary documentation to ensure concordance with the investigator rating may be repeated as many times as needed throughout the screening period.

1. After motor state recognition training, the patient will be invited to the clinic, and both the study rater and the patient will complete an “ON/OFF” home diary, at half hour intervals over a 4-hour period, to obtain concordance of >75% between the evaluations (e.g., “ON, OFF and “dyskinesia”) of the rater and the patient.
- m. After assurance of >75% concordance between the rater and patient, the patients will complete at their homes the “ON/OFF” home diary during three consecutive 24-hour periods (72 hours total) and send the completed diaries to the site (e.g., via fax, email). The patients will send the completed diaries to the site (e.g., via fax, email) up to one week before the end of the screening period because these diaries will serve as the baseline motor home diary and for eligibility to participate in the study.
- n. Prior and concomitant medication during 28 days prior to Baseline (Visit 2).
- o. The purpose of the assessment at Visit 2 is to confirm that there are no changes since Screening (Visit 1).
- p. The assessment will be performed at Visit 7/ET or at Visit 8.
- q. Vital signs include supine (after resting for at least 5 minutes), supine, and standing BP, pulse rate, and body weight.
- r. Height will be recorded at Screening (Visit 1) only.

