- ff. For patients requiring an amantadine washout period, two screening visits will be required during the screening period: Visit 1 and Visit 1.1. Visit 1, the first screening visit, will be performed up to 9 weeks/63 days prior to Baseline (Visit 2) and Visit 1.1 will be performed no later than 3 weeks/ 21 days prior to Baseline. For patients not requiring an amantadine washout period, only one screening visit will be required during the screening period: Visit 1. As much as possible, this visit should be performed 3 weeks/ 21 days prior to Baseline.
- gg. Additional visit only required for patients requiring an amantadine washout period.
- hh. If Visit 1.1 is required due to necessity for amantadine washout, this assessment shall only be performed at Visit 1.1 and not at Visit 1.

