6.2.2 UPDRS

The UPDRS scale is divided into 4 parts. Part 1 is designed to rate mentation, behavior and mood (questions 1 to 4). It is to be collected as historical information without direct relevance to “ON” or “OFF” periods experienced by the patient. Part 2 (questions 5 to 17) is designed to rate activities of daily living for both “ON” and “OFF” periods. Part 3 (questions 18 to 31) is done as a motor examination at the time of a visit. Part 4 (questions 32 to 42) is historical information designed to rate complications of therapy. The various items to be rated are scored using a 5-point system (i.e., 0 is normal and 4 indicates a severe abnormality). UPDRS Part 2 and Part 3 will be measured at the time points noted in the schedule of assessments ([Table 4](#)).

6.2.3 “ON/OFF” Home Diary Assessments

The “ON/OFF” home diary assessments are assessed during three consecutive 24-hour periods. During the screening period, potential patients and any involved caregivers or study partners if applicable will be trained to recognize the different motor states (“ON without dyskinesia,” “ON with no troublesome dyskinesia,” “ON with troublesome dyskinesia,” and “OFF”), and to complete a corresponding “ON/OFF” home diary. Training will be conducted by a well-

trained rater. After training, the patients will be invited to the clinic; the study rater and the patients will complete an “ON/OFF” diary at half-hour intervals over a 4-hour period to ensure concordance of >75% between the evaluations (e.g., “ON, OFF and dyskinesia”) of the rater and the patient. After assurance of >75% concordance between the rater and patient, the patients will complete at their homes the “ON/OFF Home Diary” during three consecutive 24-hour periods (72 hours total). The patients will send the completed diaries to the site (e.g., via fax, email) during the first two weeks of the screening period because these diaries will serve as the baseline motor home diary and for eligibility to participate in the study. Training may be repeated during the screening period to ensure concordance with investigator ratings. The assessments will be carried out at the time points noted in the schedule of assessments ([Table 4](#)).

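### The two-week deadline for the baseline diary in Protocol Section 6.2.3 cannot be met together with the 4-week amantadine-free interval in inclusion 9, and Section 3.1.1 and Table 4 differ on which washouts need Visit 1.1

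*Protocol*

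**What the plan says.** **Diary deadline.** Protocol Section 6.2.3 describes training, concordance testing and three 24-hour diaries. It then has the diaries sent to the site "during the first two weeks of the screening period because these diaries will serve as the baseline motor home diary"; they also decide eligibility. No other timing is given for washout patients, although the section closes by referring to Table 4 for time points. Table 4 footnote m instead sets the return at "up to one week before the end of the screening period", and Section 3.1.1 says the same.

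**Amantadine.** Under inclusion 9, patients on a stable daily dose of 200 mg or less "must be off this treatment at least 4 weeks prior to the assessment of UDysRS part 4"; the same interval applies before concordance testing and before the diaries. Section 5.10.1 repeats this: "Amantadine is not allowed within 4 weeks prior to the UDyRS Part 4 assessment for eligibility, concordance testing" and the diaries. Visit 1 may be as early as Day -63, and Visit 1.1 is to be no later than Day -21. Footnote hh moves training, concordance testing, diary dispensing and UDysRS Part 4 to Visit 1.1 for amantadine-washout patients and bars them at Visit 1.

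**Other prohibited drugs.** Section 3.1.1 opens its single-visit rule with "For patients not requiring a washout period for any prohibited medication". Footnote ff is wider: "For patients not requiring an amantadine washout period, only one screening visit will be required during the screening period: Visit 1". Elsewhere Section 3.1.1 itself links the second visit, and the choice of visit for training, to amantadine alone. The Anti PD/PD-LID row of Table 3 includes "topiramate, amantadine, levodopa injection/infusion", and Table 3 drugs are barred for 6 weeks before Baseline.

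**SAP.** Section 6.2.1 takes the diary before Visit 2 as baseline. If baseline days are missing or invalid, it uses the last three valid days before first dose, however long before Baseline they were recorded.

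**The concern.** The screening diary decides entry under inclusion 7. It is also the baseline for ON time without troublesome dyskinesia, ON time without any dyskinesia and OFF time, and for the OFF-time condition of the responder endpoint. A site that follows 6.2.3 literally for a patient stopping amantadine at Visit 1 would collect that diary before the interval required by inclusion 9 has passed. Change from baseline could then mix drug withdrawal with study treatment. The two halves of the responder definition could also have baselines in different drug states, since the UDysRS half starts from Visit 2.

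The protocol gives some reason to think amantadine matters. Section 1.1.3 cites differences from placebo of -7.9 and -14.4 UDysRS points for an extended-release product, against a design difference of 8.5 in Section 7.6. Those figures concern a different instrument and a different product (274 mg in the cited controlled studies, against 200 mg or less in inclusion 9). They show that the effect need not be negligible and do not size a diary bias.

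**Working it through.** The documents give no figure of their own to reproduce; the check is calendar arithmetic on their day numbers.

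**Inputs**
- 6.2.3 deadline: 14 days after screening starts.
- Amantadine-free interval: 28 days (inclusion 9, Section 5.10.1).
- Diary length: 3 days.
- Section 3.1.1 / footnote m deadline: 1 week before screening ends, taken as Day -7.
- Latest Visit 1.1: Day -21 (Section 3.1.1, footnote ff).
- Assumption: amantadine is stopped on the day of Visit 1, Day -S.

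**Formulas**
- 6.2.3 deadline = -S + 14
- Earliest permitted rating = -S + 28
- Earliest completed diary = -S + 28 + 3 = -S + 31
- Shortfall = (-S + 31) - (-S + 14) = 17 days, independent of S

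| Visit 1 | 6.2.3 deadline | Earliest rating | Diary complete | Meets 6.2.3 | Rating by Day -21 | Diary by Day -7 |
|---|---|---|---|---|---|---|
| Day -63 | -49 | -35 | -32 | no | yes | yes |
| Day -56 | -42 | -28 | -25 | no | yes | yes |
| Day -49 | -35 | -21 | -18 | no | yes | yes |
| Day -42 | -28 | -14 | -11 | no | no | yes |
| Day -35 | -21 | -7 | -4 | no | no | no |
| Day -21 | -7 | 7 | 10 | no | no | no |

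At the 6.2.3 deadline such a patient is at most 14 days off drug, against 28 required. Both rules could be met only if amantadine had been stopped at least 17 days before Visit 1. Under the Section 3.1.1 deadline the conflict goes away when Visit 1 is on Day -49 or earlier.

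**6.2.3 against Section 3.1.1.** For S of 21 or more, which is the protocol minimum, -S + 14 is never later than Day -7. Returning the diary by the 6.2.3 date therefore also satisfies Section 3.1.1, and the two dates coincide at S = 21. The deadline in 6.2.3 is stricter than that in Section 3.1.1; its real conflict is with inclusion 9.

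**Other Table 3 drugs.** The 6-week bar means stopping by Day -42. Screening may start at Day -63, which leaves 63 - 42 = 21 days in which Visit 1 can precede the required stop. Under footnote ff such a patient has only Visit 1, so the qualifying ratings scheduled there could be made on drug. At the preferred Visit 1 on Day -21, the drug would already have been stopped for at least 42 - 21 = 21 days.

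**The case against.** The strongest reply is that 6.2.3 gives nobody permission to skip the washout. It sets a date that cannot be met, while the 4-week rule stands in inclusion 9 and again in Section 5.10.1. It defers to Table 4 for time points. Under footnote hh a washout patient does not receive the diary until Visit 1.1, and the Enrollment Authorization Committee reviews eligibility before randomization. The original design figure reproduced in SAP 4.1 shows about 3 weeks of screening, so the phrase is probably left over from before screening was lengthened. Most of this stands. It makes a contaminated baseline less likely. It does not remove the contradiction: a site cannot comply with both sections, and a pointer to Table 4 does not cancel an explicit deadline in the section that governs the diary.

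A reader might infer more than the documents support:
- **That Table 4 contradicts inclusion 9.** It does not. Inclusion 9 covers amantadine only, and footnotes hh and m agree with it.
- **That 6.2.3 puts the qualifying UDysRS Part 4 too early.** The section does not time Part 4.
- **That the primary endpoint is compromised.** Its baseline is the Visit 2 UDysRS.
- **That ratings on topiramate or mucuna pruriens understate dyskinesia.** The documents do not call either drug anti-dyskinetic. The same Table 3 row also holds apomorphine and levodopa injection or infusion, so sharing the row with amantadine shows no direction of effect.
- **That Table 4 breaks a clear rule in Section 3.1.1 for other drugs.** Section 3.1.1 is itself inconsistent on this point.

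**Conclusion.** The concern holds in a limited form. Section 6.2.3 and inclusion 9 cannot both be met by a patient who stops amantadine at Visit 1. The shortfall is 17 days at any screening length, with at most 14 of the required 28 days off drug at the deadline. The result rests on the stopping day being Visit 1; a later stop widens the gap, and a stop 17 or more days before Visit 1 closes it.

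The exposure is confined to eligibility, the diary endpoints and the OFF-time part of the responder endpoint, and only where a site followed 6.2.3 rather than footnote hh. The documents do not say how many patients were affected, if any. SAP 9.3 states that the trial stopped before 30 were enrolled.

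The second part is a smaller mismatch between one sentence of Section 3.1.1 and footnotes ff, gg and hh. It has consequences only if Visit 1 falls before about Day -42 for a patient still taking a non-amantadine Table 3 drug. The documents support neither a direction nor a size for any resulting bias.

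**What to change.** 1. **Protocol Section 6.2.3.** Replace the two-week deadline with the Section 3.1.1 / footnote m deadline, and refer to Table 4 footnote hh for washout patients.
2. **Protocol Section 3.1.1 and Table 4 footnotes ff, gg and hh.** Reconcile them so that they name the same set of washouts requiring Visit 1.1. Extending the footnotes only to the Anti PD/PD-LID row would still not match the Section 3.1.1 wording on any prohibited medication. Which washouts and intervals apply is for the sponsor to settle; none is proposed here.
3. **SAP 6.2.1.** Limit the baseline-diary fallback to days that meet the protocol's washout condition. The SAP states that it is being finalized before database lock and unblinding, so this can be settled blind, together with a check of diary dates against amantadine stop dates.

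**Cost.** The protocol changes are wording. The SAP change may set a few baseline diaries to missing. With at most 29 patients enrolled, each is at least 1/29 = 3.4% of the sample, so the number should be reported. Stop dates may need retrieving from source or the Visit 1 medication history: a compliant stop is more than 28 days before Baseline, whereas Section 5.10 requires prior medication to be recorded for the 28 days before Baseline.
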